2.3.2 Protocol deviations

The number and percentage of patients with protocol deviations by category will be summarized by study phase (see Section 2.1.1 for study phase definitions). Additionally, a listing of protocol deviations during the study will also be presented. The RS will be used.

2.3.3 Demographics and other baseline characteristics

Demographics, baseline characteristics and disease history are collected at the screening visit. Descriptive summaries and/or listings will be provided. The number and percentage (categorical variables) and descriptive statistics (continuous data) for the information below will be summarized by treatment group and open-label sacubitril/valsartan.

The FAS will be used.

Demographics and baseline characteristics

Demographic variables include:

- Age (years), age group (<65, ≥65 years; and <75, ≥75 years)
- Sex (Male, Female)
 - Child bearing status (Able to bear children, Post-menopausal, Sterile)
- Race (Caucasian, Black, Asian, Native American, Pacific Islander, Other, Unknown)
- Ethnicity (Hispanic or Latino, Not Hispanic or Latino, Unknown)

General baseline characteristic variables include:

- Height (cm)
- Weight (kg)
- Body mass index (BMI) (kg/ m²) [*weight (kg)/height (m²)*]
 - BMI categories (<20, 20 - <25, 25 - 30, >30 kg/m²)
- Smoking history (Never, Current, Former)
- eGFR (ml/min/1.73 m²)

- eGFR categories (<45, 45 - <60, ≥60 ml/min/1.73 m²)
- Plasma NT-proBNP (pg/mL)
 - Plasma NT-proBNP categories (<450, 450 - <900, 900 - <1600, 1600 - <3200, ≥3200 pg/mL)
- PlasmaBNP (pg/mL)
 - Plasma BNP categories (<100, 100 - <225, 225 - <400, 400 - <800, ≥800 pg/mL)

Key hemodynamic baseline characteristic variables include:

- Aortic characteristic impedance (dyne x sec/cm⁵)
- Central (aortic) pulse pressure (mmHg)
- Carotid-femoral pulse wave velocity (m/sec), both untransformed values and negative inverse transformed values (niCFPWV = -1000/CFPWV)
- Augmentation index (%)
- Aorta-carotid reflection coefficient
- Carotid pulsatility index
- Central systolic pressure (mmHg)
- Central diastolic pressure (mmHg)
- Heart rate (bpm)

Key echocardiographic baseline characteristic variables include:

- Global longitudinal strain (%)
- Left atrial volume index (mL/m²)
- Mitral annular E' velocity (cm/sec)
- Mitral E/E'
- LVEF (%)
- Ventricular-vascular coupling (Ea/Ees)
- Left ventricular end systolic volume index (LVESVi) (mL/m²)
- Left ventricular end diastolic volume index (LVEDVi) (mL/m²)

Disease history

Disease history variables, as collected on the Heart Failure History eCRF at screening, include:

- NYHA classification [best value during the past month prior to screening visit] (I, II, III, IV)
- Primary heart failure etiology (Ischemic, Non-ischemic)

- Non-ischemic etiology (Hypertensive [No, Yes], Diabetic [No, Yes], Alcoholic [No, Yes], Myocarditis [No, Yes], Peripartum [No, Yes], Drug induced [non-chemotherapy] [No, Yes], Chemotherapy [No, Yes], Idiopathic Other [No, Yes], Valvular heart disease [No, Yes], Other [No, Yes])
- Myocardial infarction (No, Yes)
- Coronary revascularization (No, Yes)
 - Coronary revascularization type (Percutaneous coronary intervention [PCI], Coronary Artery Bypass Graft [CABG])
- Prior heart failure hospitalization (No, Yes)
 - Number of heart failure hospitalizations in the last 12 months
- Most recent ejection fraction (%)
 - Ejection fraction categories (<25%, 25% - <35%, ≥35%)
 - Method used (Magnetic Resonance Imaging [MRI], Echocardiography, Nuclear [SPECT/PET/MUGA], Ventriculogram, Other)
- ACE inhibitor intolerant (No, Yes)
- Known history of diabetes mellitus (No, Yes)
 - Controlled by: Insulin (No, Yes), Oral anti-diabetic agent (No, Yes), GLP-1 agonist (No, Yes), Diet only (No, Yes)

Cardiovascular history

Cardiovascular history will be summarized. The following disease information will be collected:

- Hypertension (No, Yes, Unknown)
- Transient Ischemic Attack (TIA) (No, Yes, Unknown)
- Stroke (No, Yes, Unknown)
- Peripheral vascular disease (No, Yes, Unknown)
- Chronic Kidney Disease (CKD) stage (CKD stage 1 [eGFR ≥90], CKD stage 2 [eGFR 60 - 89], CKD stage 3 [eGFR 30 - 59], CKD stage 4 [eGFR 15 - 29], CKD stage 5 [eGFR <15 or dialysis], No CKD)
- Arrhythmia (No, Yes, Unknown)
 - Arrhythmia type (Atrial fibrillation, Atrial flutter, Supraventricular tachycardia, Ventricular tachycardia)
- Pacemaker/Implantable Cardioverter Defibrillator (ICD) (No, Yes, Unknown)
 - Device type (Pacemaker, Cardiac resynchronization therapy - no ICD [CRT-P], Cardiac resynchronization therapy - with ICD [CRT-D], ICD only [single/dual chamber], Unknown)
- Moderate to severe valvular heart disease (No, Yes, Unknown)

- Valvular heart disease type (Mitral regurgitation, Aortic regurgitation, Aortic stenosis, Tricuspid regurgitation, Other)
- Prior valvular surgery (No, Yes, Unknown)
 - Valvular surgery type (Mitral, Aortic, Tricuspid, Pulmonic)

Non-cardiovascular medical history

Non-cardiovascular medical history and ongoing conditions will be summarized and listed. The summary will be presented by primary system organ class (SOC), preferred term (PT) and treatment group and open-label sacubitril/valsartan. Non-cardiovascular medical history and ongoing conditions will be coded using Medical Dictionary for Regulatory Activities (MedDRA) terminology (v21.1 or higher).

Surgeries and Medical Procedures

Surgeries and medical procedures will be listed. Surgeries and medical procedures will be coded using MedDRA terminology (v21.1 or higher).

2.4 Treatments (study treatment, rescue medication, concomitant therapies, compliance)

The SS will be used for all analyses associated with study treatment and medications, unless otherwise specified.

2.4.1 Study treatment / compliance

The duration of the double-blind study treatment phase is defined as:

Duration (days) = (date of last study treatment in double-blind study phase – date of first study treatment) +1

The duration of the open-label study treatment phase is defined as:

Duration (days) = (date of last study treatment in open-label study phase – date of first study treatment in open-label study phase) +1

Summary statistics will be displayed for the duration of double-blind study treatment and the duration of open-label study treatment.

The durations will also be categorized into weekly time intervals (<7 days, 7 - <14 days, 14 - <21 days, ..., etc.). The number and percentage of patients in each category will be presented by study phase.

Total patient-days of exposure will also be summarized by study phase.

In addition, the number and percentage of patients at each dose level dispensed by visit will be summarized by treatment group and open-label sacubitril/valsartan. The number and percentage of the maximum dose level dispensed will also be presented by treatment group and open-label sacubitril/valsartan. Similarly, the up-titrated doses, down-titrated doses and unchanged doses will be summarized by visit, treatment group and open-label sacubitril/valsartan.

All information on dose administration will be listed.

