Key Inclusion criteria	
 
1. Men and women ≥ 50 years of age.
 
2. History of HTN and one of the following at BOTH screening and pre-randomization: 
 
a. SBP > 105 mm Hg on antihypertensive medication.
 
b. SBP ≥ 140 mm Hg and NOT on antihypertensive medication.
 
 
 
3. NYHA class I-III heart failure and with a reduced ejection fraction ≤ 40%.
 
4. On stable doses of treatment with guideline-directed therapy, other than ACEis and ARBs prior to randomization.
 
5. On an optimal medical regimen of diuretics and background medications to effectively treat co-morbidities such as HTN, DM, and coronary artery disease
 

Key Exclusion criteria	
 
1. History of hypersensitivity to any of the study drugs, including history of hypersensitivity to drugs of similar chemical classes, or allergy to ACEis, ARBs, or NEP inhibitors as well as known or suspected contraindications to the study drugs.
 
2. Previous history of intolerance to sacubitril/valsartan, ACEi or ARB standard of care doses despite appropriate and gradual up-titration.
 
3. History of angioedema, drug-related or otherwise.
 
4. Requirement of treatment with both ACE inhibitor and ARB.
 
5. Current or prior treatment with sacubitril/valsartan
 

Study treatment	
All eligible patients will be randomized to receive either sacubitril/valsartan or enalapril. The following study treatment will be provided for the 12-week double blind double dummy treatment epoch:
 
 
• sacubitril/valsartan tablets + matching placebo, or;
 
• enalapril tablets + matching placebo.
 
 
All patients will begin on Dose Level 1 and will be titrated every 2 weeks to target Dose Level 3. Safety and tolerability is monitored. Down-titration to temporary withdrawal of study treatment is permitted. Rescue option is available for worsening heart failure.
 
Sacubitril/valsartan tablets will be provided for the 12-week open label extension. All dose levels are available. Target is Dose Level 3.

Efficacy assessments	Primary (Week 12)

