**3. Further Adjust Study Treatment Dose Level**

- If tolerability issues are not alleviated despite down-titration by one dose level, the investigator may down-titrate further to the next lower study treatment dose level. The patient may continue receiving the lower dose level for a recommended period of one to a maximum of 4 weeks, up to a temporary withdrawal of study treatment. See Step 5.
- Again, once stable, the patient should be re-challenged with up-titration to the next higher dose level in an attempt to gradually bring the patient back to the target study treatment dose level (Dose Level 3).
- The investigator may choose the next dose level for down- or up-titration according to his or her clinical judgment.

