## 5. Study drug restart after temporary treatment interruption

- Once the investigator considers the patient's condition appropriate for receiving the study drug, the investigator should re-start the patient on study treatment at the most appropriate and allowable dose level per his/her medical judgment.
- If tolerated, the patient should be titrated up to the next dose level every 1 to 4 weeks, as per the investigator's judgment.
- In some instances, Dose Level 1 or 2 could be maintained if the investigator considers that the patient's condition would not allow any further up-titration to the target dose of study medication (Dose Level 3). In this case, it would be acceptable to maintain the patient at Dose Level 1 or 2, whichever is the higher and tolerated dose level by the patient, but reasons for not getting to Dose Level 3 need to be captured in the eCRF.
- Should the patient not tolerate the re-start study drug dose level, he/she may be down-titrated again (if appropriate) or discontinued from study treatment.

Patients re-started on the study drug will retain their original randomization and study identification numbers.

The IRT must be contacted to register any changes in the patient's study treatment dose level, including in cases of temporary and permanent withdrawal or re-start of the study drug, and to obtain the medication numbers of the study drug supplies required for the new study treatment dose level. All dose changes and interruptions must also be recorded on the Dosage Administration Record eCRF.

Study visits should occur as close as possible to the pre-defined visit and time schedule described in [Table 6-1](#). The timeframe between the regular visits should be maintained as scheduled, irrespective of the number of unscheduled visits that may be performed in between, or dose interruptions that may occur.

In case of pregnancy discovered during the study, the patient should be instructed to stop taking the study drug immediately. (See [Section 6.5.6](#) and [Section 7.6](#))

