## 6.3 Treatment exposure and compliance

Compliance will be assessed by the investigator, and/or study personnel, at each visit using pill counts and information provided by the patient. This information should be captured in the source document at each visit. All study treatment dispensed and returned must be recorded in the Drug Accountability Record.

Patient compliance should be at least 80% during the double-blind treatment period. The investigator and/or study personnel will counsel the patient if compliance is below 80%. Study drug accountability will also be determined by the site monitor while performing routine site visits and at the completion of the study.

Duration of double-blind study drug exposure will be calculated based upon the start and end dates recorded in the Dosage Administration Record eCRF.

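### SAP 2.4.1 counts days of temporary interruption as exposure, which overstates double-blind patient-days in the descriptive exposure tables

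*SAP*

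**What the plan says.** SAP 2.4.1 gives one formula per phase. Double-blind: "Duration (days) = (date of last study treatment in double-blind study phase – date of first study treatment) +1". Open-label: "Duration (days) = (date of last study treatment in open-label study phase – date of first study treatment in open-label study phase) +1". The durations are summarised and grouped into weekly categories. The section then adds "Total patient-days of exposure will also be summarized by study phase" and offers no other definition of exposure.

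The protocol expects gaps in treatment. Its summary states "Down-titration to temporary withdrawal of study treatment is permitted", and step 3 of Section 5.5.5 lets down-titration go "up to a temporary withdrawal of study treatment". Step 5 of that section describes restarting the drug and requires that "All dose changes and interruptions must also be recorded on the Dosage Administration Record eCRF".

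Protocol 6.3 says that the duration of double-blind exposure "will be calculated based upon the start and end dates recorded in the Dosage Administration Record eCRF". It is silent on days off drug between those dates.

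Two date rules in SAP 2.1.1 also matter. The last double-blind dose is taken first from the Visit 6 form. The first open-label dose is taken from the Visit 7 form.

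**The concern.** A reader takes patient-days of exposure to mean days on drug. The SAP quantity is elapsed time from first to last dose. The two agree for patients treated without a break and for patients who stop for good, since the last dose date then ends the span correctly. They differ for a patient who stops and restarts. Under Protocol 5.5.4 the final double-blind dose is given in clinic at Visit 6, so a patient who restarts at any time before that visit and attends it is credited with the whole phase, however long the gap.

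No other planned summary shows the missing time. SAP 2.8.1.3 counts patients with adverse events that led to dose adjustment or interruption, with the two pooled and no days attached. Dose levels in SAP 2.4.1 are those dispensed. Pill-count information is kept in source documents (Protocol 6.3). Individual dosing records are only listed. At stake is whether the one planned aggregate of time on drug means what its label says, in a forced-titration trial where tolerability is a stated assessment.

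**Working it through.** The documents state no exposure figure, so there is nothing to reproduce. The check compares the SAP span with the same span less off-drug days.

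**Inputs**
- Double-blind span: Day 1 to Day 84 (Protocol Table 6-1), so 84 − 1 + 1 = 84 days.
- Planned number randomised: 432 (Protocol 9.8, SAP 1.1).
- Share of patients with an interruption, f: not in the documents; assumed 5-20%.
- Length of an interruption, L: not in the documents; assumed 7-28 days. Protocol 5.5.5 sets no maximum for time off drug. Its limit of 4 weeks applies to time on a lower dose level and is not the source of the 28 days.

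**One patient.** Overstatement = L / (84 − L).
- 7 days: 7/77 = 9.1%
- 14 days: 14/70 = 20.0%
- 28 days: 28/56 = 50.0%

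**Whole trial, double-blind.** If all 432 patients have full spans, the SAP total is 432 × 84 = 36,288 patient-days. Excess days = 432 × f × L. Overstatement relative to net exposure = fL / (84 − fL); the number of patients cancels.

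| f | L = 7 | L = 14 | L = 28 |
|---|---|---|---|
| 5% | 0.42% | 0.84% | 1.69% |
| 10% | 0.84% | 1.69% | 3.45% |
| 20% | 1.69% | 3.45% | 7.14% |

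At the lowest corner the excess is 432 × 0.05 × 7 = 151 patient-days. At the highest it is 432 × 0.20 × 28 = 2,419. Each off-drug day inside the span adds one day to the SAP figure and none removes a day, so the error has one direction.

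**Open-label.** Drug is dispensed at Week 12 and started on the evening of the following day (Protocol 3.1), about Day 85. Visit 7 is Day 98 and the last visit is Day 168.
- Span from Day 85: 168 − 85 + 1 = 84 days.
- Span from Day 98: 168 − 98 + 1 = 71 days.
- Difference: 13 days, or 13/84 = 15.5%.

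If the Visit 7 form supplies the date of the dose given at that visit, up to about 13 days per patient are lost. If it captures the true first open-label dose, none are. The SAP text does not settle which. The interruption error has the same form as before, but the net direction is open.

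**The case against.** The best defence is that the SAP follows the protocol. Protocol 6.3 bases duration on start and end dates, and Protocol 9.3 asks for overall duration on double-blind drug. First-to-last-dose time is a coherent descriptive measure. Reading patient-days as the sum of those durations is also an inference, because the SAP gives that quantity no formula. This much stands: the duration measure can stay. It does not rescue the exposure label, since summed durations are the only basis the text offers and neither document says that interruptions are included.

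Three stronger readings are tempting, and the documents do not support them.

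- *Patient-days is the denominator of the safety analysis.* The tables in SAP 2.8.1 to 2.8.4 report numbers and percentages of patients. Hyperkalaemia, worsening renal function and hypotension are incidences with relative risks. The negative binomial model named in the SAP's amendment history uses log study duration through Week 12, not time on drug.
- *The error favours the less well tolerated arm.* Protocol 3.6.1 does show more hypotension on sacubitril/valsartan in PARADIGM-HF (17.61% against 11.97%). It also shows more hyperkalaemia on enalapril (14% against 11.61%) and more renal dysfunction on enalapril (11.52% against 10.14%). These are event rates from another trial, not interruption rates. Here, concomitant drugs are adjusted and the dose lowered before drug is withdrawn.
- *Tolerability of titration is hidden.* SAP 2.3.1 reports patients reaching or not reaching Dose Level 3, with reasons, and premature discontinuations. SAP 2.4.1 reports dose levels by visit and up- and down-titrations. SAP 2.8.1.3 counts events leading to dose adjustment or interruption. What lacks a summary is the length of interruptions.

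**Conclusion.** The point holds as a small correction to a descriptive figure. As written, SAP 2.4.1 counts off-drug days as exposure whenever a patient interrupts and restarts, although the data needed to remove them are collected.

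In the double-blind phase the direction is certain. The individual effect is 9% to 50% for gaps of 7 to 28 days. The effect on the total is 0.4% to 7.1% and rests wholly on the assumed rates and lengths. The primary and secondary results and the visible safety estimates are unaffected.

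A reader might infer that open-label exposure is overstated as well. That is secure only for the interruption component, because the Visit 7 date rule could remove more days than interruptions add.

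**What to change.** In SAP 2.4.1:

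1. Define net exposure as (last dose date − first dose date + 1) minus the interruption days recorded on the Dosage Administration Record, and use it for patient-days in each phase.
2. Keep the present formula, labelled *duration from first to last dose, including interruptions*, and state which measure the weekly categories use.
3. Summarise the number and length of interruptions by arm.
4. Reconcile the open-label first-dose rule in SAP 2.1.1 (Visit 7 form) with dispensing at Week 12 in Protocol 5.5.4, so that the span begins at the actual first open-label dose.

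The cost is some SAP wording, one small derivation and one added summary, all from data already required on the eCRF. Double-blind exposure figures will be slightly lower.

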2.4.2 Prior, concomitant and post therapies

Prior and concomitant medications will be coded according to the World Health Organization (WHO) Drug Reference List (WHO Drug v2017 Nov or later). Prior and concomitant medications are mutually exclusive, as defined below:

- A prior medication is defined as any medication with an end date prior to the first dose of study treatment.
- A concomitant medication is defined as any medication taken on or after the start of study treatment. A prior medication that is ‘ongoing’ at the time of the first study treatment or whose end date is after first study treatment will be considered a concomitant medication.

The number and percentage of patients with prior medications will be summarized by Anatomical Therapeutic Chemical (ATC) class, preferred term (PT) and treatment group, and open-label sacubitril/valsartan. Separate summaries of prior CV, HF, ACEi and ARB medications will also be produced. Concomitant medications will be summarized in a similar fashion. All medications will be listed.

The number and percentage of patients in the following prior ACEi/ARB exposure categories (assessed at screening) will be summarized:

- ACEi/ARB naïve (never exposed)
- Previously on ACEi/ARB but not currently taking (previously exposed)
- Currently taking

2.5 Analysis of the primary objective

2.5.1 Primary endpoint

The primary endpoint is the change in aortic characteristic impedance ($Z_c = dP/dQ$) between baseline and Week 12. The analysis of the primary endpoint will be based on the FAS.

2.5.2 Statistical hypothesis, model, and method of analysis

Let μ_j denote the population mean of change from baseline in the aortic characteristic impedance at Week 12 for treatment group j , $j = 0, 1$, where 0 corresponds to enalapril and 1 corresponds to sacubitril/valsartan.

The following null hypothesis (H_0) will be tested against the alternative hypothesis (H_A):

$$H_0: \mu_1 - \mu_0 = 0$$

$$H_A: \mu_1 - \mu_0 \neq 0$$

The primary endpoint will be analyzed by an analysis of covariance (ANCOVA) model with treatment and Z_c baseline as explanatory variables (Mitchell 2002). The least squares means of the two treatment groups, least squares mean difference of the treatment groups, 95% confidence interval for the difference in the two treatment groups, and p-value based on the fitted linear model will be reported. If the p-value is < 0.05 and the least squares mean difference

of the treatment groups favors sacubitril/valsartan, statistical significance in favor of sacubitril/valsartan is shown.

